### **5.4. Per-Protocol Set**

The Per-Protocol Set (PPS) is a subset of the FAS. It will be the analysis population for sensitivity analyses that will be conducted for the primary and key secondary efficacy endpoint analyses and will be summarized using treatment as randomized. Any subject affected by a significant protocol deviation that might affect the primary efficacy analysis will be excluded from the PPS. The PPS will be identified before the unmasking of treatment assignments.

Before the unmasking of treatment assignment, Santen's study team will review all protocol deviations, identify subjects with any protocol deviation that could affect the efficacy outcome, and determine whether or not to exclude the subject from the PPS.

## 6. GENERAL CONSIDERATIONS

All measures will be summarized by treatment (planned or actual received) descriptively. Continuous variables will be summarized using descriptive statistics such as number of observations (n), mean, standard deviation, median, minimum, and maximum. Categorical variables will be tabulated using frequency (n) and percent (%).

The statistical testing will be conducted at a significance level of 0.05 (two-sided) and the 95% confidence interval will be shown, unless specified otherwise. No statistical testing will be conducted for safety measures.

All data manipulations, descriptive summaries, and statistical hypothesis testing will be performed using Statistical Analysis System (SAS) Version 9.4 or later.

### 6.1. Adjustments for Covariates

In general, the inferential analysis of each IOP endpoint will adjust for the baseline IOP. Detailed information on covariate adjustment is provided in [Section 8.1](#).

## 6.2. Handling of Missing Data

### 6.2.1. Efficacy Measures

For subjects with the use of any non-study IOP-lowering therapy to lower IOP, unless otherwise specified, the IOP data collected after the non-study IOP-lowering therapy will be censored (treated as missing) in efficacy analyses in both double-masked and open-label periods.

For efficacy measures during double-masked period,

- For each IOP endpoint, no imputation is needed for the analysis on observed cases using the mixed-effects model for repeated measures (MMRM). Sensitivity analysis will be performed using a Pattern-Mixture Model (PMM) approach.
- In the PMM approach, Multiple Imputation (MI) with mixed missing data mechanisms will be used to investigate the appropriateness of the missing at random (MAR) assumption for missing values resulting from censoring due to the use of IOP-lowering rescue therapy, or resulting from study discontinuation due to lack of efficacy or AE.

For efficacy measures during open-label treatment period, no inferential analysis will be performed. Summary statistics will be provided for IOP and mean diurnal IOP for each scheduled visit, using observed data.

### 6.2.2. Safety Measures

Descriptive summaries of safety measures will be based on observed data only. No imputation of missing scores will be implemented.

### 6.2.3. Dates for Medical Events and Medications

Completely or partially missing onset and resolution dates of medical history (MH), AE, and concomitant medications (CM) will be imputed as follows ([Table 7](#)):

**Table 7: Handling of Missing Date for Medical Events and Medications**

| Date  | Type of Missing Date                         | Handling of Missing Date   |
|---|--|--|
| Event onset date
(e.g., YYYY-MM-DD)      | Completely missing                           | No imputation will be applied:
For AE, the event will be considered treatment emergent.
For CM, the event will be considered concomitant.
For MH, the event will be considered to occur prior to Inform Consent date. |
|   | Only YYYY is available                       | Use the first date of YYYY to impute the missing month and day of the onset date.  |
|   | YYYY and MM are available, but DD is missing | Use the first date of MM to impute the missing day of the onset date.  |
| Event resolution date
(e.g., YYYY-MM-DD) | Completely missing                           | No imputation will be applied. The event will be considered ongoing (i.e., not resolved) at the last visit date.   |
|   | Only YYYY is available                       | Use the last date of YYYY to impute the missing month and day of the resolution date.  |
|   | YYYY and MM are available, but DD is missing | Use the last date of MM to impute the missing day of the resolution date.  |

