## 4.4. Safety-Related Definitions

### 4.4.1. Adverse Event

Under Protocol 011709IN, an AE is defined as any untoward medical occurrence that occurs in a study subject, regardless of the causal relationship with the study treatment. An *on-study* AE can occur any time after the date of informed consent through the last study visit. An AE will be considered as *treatment-emergent* if the onset date of the AE occurred on or after the treatment start date till up to 2 days (twice the scheduled dosing interval) after treatment end date.

Treatment-emergent AEs (TEAEs) are a subset of on-study AEs. Both on-study and TEAEs will be collected, but only TEAEs will be tabulated.

The severity of each AE will be graded by the Clinical Investigator as Mild, Moderate, or Severe. AEs will also be rated by the Investigator as to their causality/relationship to the study drug.

Each AE will be classified into a system organ class (SOC) and coded to a preferred term (PT) using Medical Dictionary for Regulatory Activities (MedDRA), Version 21.1 published in 2018.

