## 4.5. Other Definitions

### 4.5.1. Prior and Concomitant Medications

Non-study medications will be categorized into prior medications and concomitant medications. Specifically, *prior medication* is defined as any non-study medication taken and ended prior to the study medication start date. *Concomitant medication* is defined as any non-study medication taken concurrently while receiving study medication, i.e., the treatment period (period of time from first dose to last dose) of a concomitant medication taken by a subject must overlap with the treatment period (period of time from first dose to last dose) of the study medication.

All prior and concomitant medications will be coded using the World Health Organization (WHO) Drug Global, Version September 2018, format B3. Each prior or concomitant medication will be classified using the Anatomical-Therapeutic-Chemical (ATC) classification system and mapped to a WHO Drug preferred drug name.

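### SAP Table 7 classes a medication with no start date as concomitant, and an AE with no onset date as treatment-emergent, even when the known stop date precedes first dose, contradicting SAP 4.5.1 and 4.4.1

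*SAP*

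**What the plan says.** SAP 6.2.3 introduces Table 7 with the words "Completely or partially missing onset and resolution dates of medical history (MH), AE, and concomitant medications (CM) will be imputed as follows". In the row for a completely missing onset date no date is imputed and the class is assigned directly: "For AE, the event will be considered treatment emergent" and "For CM, the event will be considered concomitant". The row sets no condition on the stop or resolution date. Other rows deal with partial dates. A partial onset date goes to the first day of the known year or month, and a partial resolution date to the last day. A completely missing resolution date means the event is treated as ongoing.

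The classes themselves are defined elsewhere in the SAP:

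- **Prior medication (4.5.1):** it "is defined as any non-study medication taken and ended prior to the study medication start date".
- **Concomitant medication (4.5.1):** its period of use "must overlap with the treatment period (period of time from first dose to last dose) of the study medication".
- **Treatment-emergent AE (4.4.1):** an AE qualifies "if the onset date of the AE occurred on or after the treatment start date till up to 2 days" past the treatment end date.

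AE collection starts before dosing: "An *on-study* AE can occur any time after the date of informed consent through the last study visit". Protocol 14.5 asks for conservative imputation of missing AE and medical-history dates and applies the same rules to non-study medications.

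**The concern.** A known stop date before first dose settles the class without any start date. The medication ended too early to overlap study treatment, and the AE resolved too early to have begun on treatment. Table 7 nevertheless assigns the opposite class, and the SAP does not say whether Table 7 or the definition prevails.

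This design can produce such records. Subjects on IOP-lowering drugs stop them at screening under a washout directed by the site, so the stop date should be well documented. The start date of a long-standing drop depends on the subject interview (Protocol 21.3.1) and may be unknown.

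What is at stake is the content of the prior and concomitant medication tables (SAP 7.5) and of the AE tables, since SAP 4.4.1 tabulates only treatment-emergent events. A washed-out IOP-lowering drug in the concomitant table would read as use of a drug class that Protocol 9.2.1 prohibits during the study.

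**Working it through.** The plan states no figure on this point, so there is none to reproduce. The check applies each rule to the same records.

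**Inputs.** The start or onset date is wholly missing. First dose is Day 1. By SAP 4.1.3, a date 28 days before first dose is Day −28. The stop or resolution day is varied across the screening period (up to 35 days, Protocol 7.1) and into treatment.

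| Stop or resolution day | Medication: Table 7 | Medication: 4.5.1 | AE: Table 7 | AE: 4.4.1 |
|---|---|---|---|---|
| −35, −28, −7, −1 | concomitant | prior | treatment-emergent | cannot be treatment-emergent |
| 1, 43 | concomitant | overlap possible | treatment-emergent | possible |
| missing | concomitant | taken as ongoing, so concomitant | treatment-emergent | possible |

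**Reasoning for the first line.** For a medication, 4.5.1 needs only the end date to call it prior, and a stop before Day 1 also rules out the overlap that a concomitant medication requires. For an AE, onset cannot be later than resolution. With resolution before Day 1, onset is before Day 1 and 4.4.1 is not met.

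**Where the conflict lies.** It is confined to the first line: start wholly missing and stop before first dose. In the other lines Table 7 is a reasonable default.

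**Consistency within Table 7.** Take a prostaglandin analogue stopped at Visit 1, 28 days before Day 1. If only the start year is known, the start is set to 1 January of that year and the Day −28 stop makes the drug prior. If the year is also unknown, the same stop date gives concomitant. Losing one further item about the start reverses the class, although the start does not decide it.

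**Does the row reach these drugs?** Table 7 labels its medication category as concomitant medications. If that meant only drugs already classed as concomitant, the sentence would decide nothing. It has effect only when applied to drugs not yet classed, and Protocol 14.5 speaks of non-study medications generally.

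**The case against.** The strongest reply is that 4.5.1 defines prior medication by when it ended. A programmer who applies that definition first would class the drug as prior and never reach the Table 7 default. On this view the gap is an unstated order of precedence. That is a fair account of how the tables might come out right in practice. It does not remove the contradiction, because Table 7 states its rule without condition and nothing subordinates it to 4.5.1.

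The second reply is that such records should be rare, and this stands. The protocol requires start and stop dates for concomitant medication (9.2) and for glaucoma or OHT drugs used within 28 days before Visit 1 (21.3.1). A subject who recalls only the year falls in a different row and is classed correctly. The AE case is rarer still: the event must begin and end within a screening period of up to 35 days, AEs are queried at Visit 2 and at any Visit 1a, and yet not even an onset year is recorded.

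The third reply is that calling an AE treatment-emergent is conservative, as Protocol 14.5 intends. That holds while timing is uncertain. Once resolution is known to precede first dose, no uncertainty about treatment emergence remains.

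A reader might also infer that a washed-out drug flagged as concomitant would be taken for rescue, so that valid IOP values would be lost from the primary analysis under SAP 6.2.1: "the IOP data collected after the non-study IOP-lowering therapy will be censored (treated as missing) in efficacy analyses". The documents do not support this. Nothing links that rule to the Table 7 class. Censoring needs a time of use, and this row imputes no date. SAP 8 describes the values censored as those following rescue therapy, and Protocol 14.7 refers to data collected after study medication is stopped.

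**Conclusion.** The point holds as an error in a stated rule. For records with a wholly missing start date and a known stop or resolution date before first dose, Table 7 gives a class that SAP 4.5.1 and 4.4.1 rule out.

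The documents give no count of such records, and the number may be small or zero. Any headcount would rest on invented rates for pre-treatment and for unknown start dates, so none is offered. It would also go too far to say that washed-out glaucoma drugs will in general be reported as on-study therapy. That follows only for drugs with no start year at all, and only if Table 7 is programmed literally.

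The shown effect is limited to the descriptive medication and AE tables. SAP 6 specifies no statistical testing of safety measures, and no effect on the primary analysis is shown. The conclusion assumes that the medication entry in Table 7 covers non-study medications generally, as Protocol 14.5 indicates.

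**What to change.** In the completely-missing onset row of SAP Table 7, make the default conditional:

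- If the known or imputed stop or resolution date is missing, or is on or after the treatment start date, the medication is concomitant and the AE is treatment-emergent.
- Otherwise the medication is prior and the AE is not treatment-emergent.

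Using an imputed stop date is safe here. Table 7 moves partial stop dates to the last possible day, so an imputed date before first dose means that the true date is too.

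The cost is one sentence in the SAP and one programming condition, with no new data. No change to the censoring rule is needed on this ground.

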14.5. Handling of Missing Values

The primary analysis of continuous IOP endpoints will be performed using the MMRM analysis on observed cases. As sensitivity analyses, a last-observation-carried-forward (LOCF) approach and a Pattern Mixture Models (PMM) approach may be applied to evaluate the impact of missing data on the primary analysis results. For the binary IOP endpoints, the missing data at Month 3 will be imputed using an LOCF approach.

For medical events including AEs and medical history, completely or partially missing onset and resolution dates will be imputed in a conservative fashion. Same rules will be followed to impute the completely or partially missing start and end dates of non-study medications.

Unless specified otherwise, descriptive summaries will be based on observed cases.

More details on handling of missing data will be provided in the SAP.

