### 9.1. Adverse Events

AEs, SAEs, SARs, serious SARs, and significant AEs (AEs leading to study drug discontinuation and AEs leading to death) will be tabulated by type of AEs by treatment arm using actual treatment received for all AEs, ocular AEs, and non-ocular AEs separately.

Besides the overall AE summary, AEs, SAEs, SARs, serious SARs will be tabulated by SOC and preferred term for all AEs, ocular AEs, and non-ocular AEs separately. A subject who experienced multiple AEs within a SOC or preferred term will be counted only once for that SOC or preferred term. Non-serious AEs (including number of events) and ESIs will also be summarized by SOC and preferred term.

All the AE summaries will be performed for double-masked, open-label, and entire study periods separately. For double-masked period summaries, overall AE summary, summary of AE by SOC and PT, SAEs, SARs, and serious SARs will also be tabulated on pediatric subjects separately. For open-label and entire study period summaries, tabulations by treatment received during double-masked period will be provided as well as overall summary for subjects exposed to DE-117. So, for subjects who exposed to the Timolol arm during the double-masked period, their AE summaries under the Overall DE-117 column will be those AEs that started during the open-label treatment period.

AEs, SAEs, SARs, serious SARs, ocular AEs, AEs leading to death, AEs leading to study drug discontinuation, non-TEAEs, and ESIs, if any, will be listed separately.

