#### 9.1.1. Ocular Inflammation

Subjects who developed AEs during the study with one of the following preferred terms will be included in the ocular inflammation summary:

- Anterior chamber cell
- Anterior chamber flare
- Eye inflammation
- Anterior chamber inflammation
- Iridocyclitis
- Iritis

- Uveitis

Other preferred terms might be added upon review of the AE data before database lock.

Ocular inflammation leading to study drug discontinuation, requiring steroid treatment, or requiring NSAIDs treatment will be summarized at the subject level by frequency and percentage separately.

Ocular inflammation start time (in terms of study day) and duration of the AE will be summarized at the eye level using mean, standard deviation, median, minimum, and maximum by study eye and fellow eye separately. To allow for the computation of simple descriptive statistics, only subjects who develop ocular inflammation during the study will be used for the ocular inflammation start time summary, and only subjects who develop these AEs during the study and later resolved will be used in the duration of AE analysis.

The aforementioned summaries will be performed at the eye level. All ocular inflammation AEs will be provided in a listing.

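### SAP Table 7 back-dates a partial AE onset without checking it against first dose, so some on-treatment AEs leave the TEAE tables

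*SAP*

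**What the plan says.** SAP Section 6.2.3 applies one date rule to medical history, AEs and concomitant medications. Its Table 7 has three onset rows:

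- Day missing: "Use the first date of MM to impute the missing day of the onset date".
- Month and day missing: "Use the first date of YYYY to impute the missing month and day of the onset date".
- Date completely missing, no imputation: "For AE, the event will be considered treatment emergent".

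SAP Section 4.4.1 makes an AE treatment-emergent only if onset falls between the treatment start date and 2 days after treatment end. SAP Table 3 defines treatment start as the first double-masked dose. Section 4.4.1 adds: "Both on-study and TEAEs will be collected, but only TEAEs will be tabulated". AEs that fail the definition go to a listing (SAP Section 9.1: "non-TEAEs, and ESIs, if any, will be listed separately"). On reporting periods, Section 9.1 says: "All the AE summaries will be performed for double-masked, open-label, and entire study periods separately".

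Protocol Section 14.5 sets the principle that "completely or partially missing onset and resolution dates will be imputed in a conservative fashion", and leaves the detail to the SAP.

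**The concern.** AE incidence is a named safety endpoint, and the TEAE tables are where it is reported. The rule fails at the one boundary that decides whether an event is counted. The first of the month, or 1 January, precedes first dose for almost every subject, and nothing in either document stops the imputed date from crossing that line. Among partial dates, the loss falls mainly on the first weeks of dosing, inside the only randomized, masked comparison.

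Two side effects follow.

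- **Special summaries.** The ocular inflammation summary takes "Subjects who developed AEs during the study with one of the following preferred terms will be included in the ocular inflammation summary". The macular edema and cosmetic-change summaries are worded alike. None repeats the treatment-emergent condition, so a back-dated event may drop out, or may enter a start-time summary with a negative study day under SAP Section 4.1.3. The SAP does not say which.
- **Month 3 switch.** The same rule can move an open-label AE dated only to the month of the switch into the double-masked period. For a timolol-arm subject the event then leaves the Overall DE-117 column, which takes only AEs that began in the open-label period (SAP Section 9.1).

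**Working it through.** The documents give no figure for this rule, so there is none to reproduce.

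**One subject (assumed first dose 15 August 2018).**

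| Onset as recorded | Imputed onset | Study day (SAP 4.1.3) | Treatment-emergent? |
|---|---|---|---|
| Aug 2018 | 1 Aug 2018 | 1 − 15 = −14 | No |
| 2018 | 1 Jan 2018 | −226 | No |
| Sep 2018 | 1 Sep 2018 | 17 + 1 = 18 | Yes |
| nothing | none | none | Yes |

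Over the 365 first-dose dates of a non-leap year, an on-treatment AE dated to the first-dose month is lost for 353 (96.7%). One dated to the first-dose year is lost for 364 (99.7%). The exceptions are dosing on the 1st of a month and on 1 January.

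**Share of day-missing TEAEs lost, by hand.** Assume a 30-day month, first dose equally likely on each day j, and uniform onset. Days j to 30 are on treatment and in the first-dose month, and are lost when j ≥ 2:

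(29 + 28 + … + 1) / 30 = 435 / 30 = 14.5 days per subject.

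- Masked period, 91 days: 14.5 / 91 = 15.9%.
- Study days 1 to 8: (22 × 8 + 28) / (30 × 8) = 204 / 240 = 85.0%.
- To Day 361: 14.5 / 361 = 4.0%.
- Onsets after Day 91: none, because they cannot share a month with first dose.

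**By enumeration.** The Synopsis gives a study period of about 19 months. Subtracting 12 months of treatment and up to 5 weeks of screening leaves about 6 months for accrual. I used six 183-day windows, starting on the 1st of August 2018 through January 2019; the calendar start is an assumption.

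| Recorded onset | Onset period | TEAEs lost |
|---|---|---|
| Day missing | 91 days | 16.1% to 16.4% |
| Day missing | days 1 to 8 | 84.7% to 85.7% |
| Day missing | 12 months | 4.0% to 4.1% |
| Year only | 91 days | 74.9, 74.9, 74.9, 77.5, 85.5, 99.5% |
| Year only | 12 months | 33.2, 41.7, 50.0, 58.5, 66.8, 75.3% |

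**Month 3 switch.** Open-label days run from Day 91 to Day 361, about 270 days. By the same argument, 14.5 / 270 = 5.4% of day-missing open-label AEs are moved into the masked period.

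**Price of a floor at first dose, if no recorded data help.** Pre-dose days sharing the first-dose month also average 14.5. With 35 days of screening, 14.5 / 35 = 41.4% of day-missing pre-dose AEs become treatment-emergent (enumeration: about 42%). With 1 day it is 29 / 30 = 96.7%.

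**The case against.** **Net count.** At an equal daily AE rate, a floor recovers about 14.5 on-treatment days per subject and, with 35-day screening and no other information, wrongly admits about 14.5 pre-dose days. AEs are collected from consent, so pre-dose events will exist. This stands. The case for a floor rests on direction: an ambiguous event is counted rather than dropped, as the SAP already chooses when the onset is wholly missing.

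**Meaning of conservative.** Protocol Section 14.5 does not define the word. Earliest onset with latest resolution gives the longest duration, a defensible meaning for a shared rule. So a reader might infer that Table 7 contradicts the protocol, but the text does not support that. It supports only that the rule is not cautious for counting TEAEs.

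**Year-only dates.** A reader might infer that every partial onset matching first dose should simply be set to that date. For year-only dates this creates a new error. Adults move to open-label DE-117 at Month 3, often in the same calendar year. With the six-month windows and uniform onset, about 20% to 68% of year-only open-label AEs would become day-1 masked events. For timolol-arm subjects, an event on open-label DE-117 would then be tabulated under timolol and lost from the Overall DE-117 column. This objection stands in full. Day-missing dates do not share the problem, because Visit 5 falls at Day 84 at the earliest and cannot be in the first-dose month.

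**Weight.** AEs are queried at every visit, eCRFs are due within 3 business days where possible (Protocol Section 18.2.3), and SAEs, ocular AEs and AEs leading to discontinuation have their own listings. This also stands.

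**Conclusion.** The rule is wrong as written, and the point is minor. The classification error follows directly from Table 7 and the TEAE definition, and no other text in either document sets a floor or an override. The percentages are shares of partially dated AEs, not of all AEs, and rest on uniform onset and an assumed accrual calendar. The number of partial dates is not given and is probably small.

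A reader might also infer that the safety comparison between arms is biased, or that events vanish from the report. The documents support neither. The rule applies alike to both arms, SAP Section 6 allows no testing of safety measures, and affected events remain in listings.

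**What to change.** Give AEs their own onset rows. Leave the medical-history and medication rows unchanged; concomitance is defined by overlap with treatment (SAP Section 4.5.1), so an early start does no harm there.

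1. **Day missing.** If the known month and year match those of first dose, impute the treatment start date, unless the resolution date or other recorded data show onset before first dose.
2. **Year only.** If the known year matches that of first dose, classify the AE as treatment-emergent in the entire-study tables unless recorded data show earlier onset. Do not automatically set onset to first dose. Assign the double-masked or open-label period from recorded data, such as the resolution date or, where available, the visit of entry. Flag the event if the period cannot be determined, and leave it out of start-time summaries.
3. **Month 3 switch.** For AEs dated only to the month of the switch, apply the same check at the open-label start, using recorded data to assign the period.

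The cost is a split of two table rows and a change to the AE derivation program; no hypothesis or efficacy analysis changes. The exceptions can use only what was recorded, and the AE attributes listed in Protocol Section 12.1.1.2 do not include the visit of first report. Where nothing helps, some same-month pre-dose AEs will count as treatment-emergent, within the range worked out above (about 42% to 97% of day-missing pre-dose AEs, depending on screening length).

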### **9.1.2. Macular Edema**

Subjects who developed AEs during the study with one of the following preferred terms will be included in the macular edema summary:

- Macular edema
- Cystoid macular edema

Macular edema start time (in terms of study day) and duration of the AE will be summarized using mean, standard deviation, median, minimum, and maximum by study eye and fellow eye separately. To allow for the computation of simple descriptive statistics, only subjects who develop macular edema during the study will be used for the macular edema start time summary, and only subjects who develop these AEs during the study and later resolved will be used in the duration of AE analysis.

Change from baseline in BCVA at the onset of macular edema, when macular edema is resolved, and at the last visit will be summarized using mean, standard deviation, median, minimum, and maximum by study eye and fellow eye separately. Pseudophakic eyes or phakic eyes at baseline who developed macular edema during the study will be summarized by frequency and percentages separately.

The aforementioned summaries will be performed at the eye level. All macular edema AEs will be provided in a listing.

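### SAP Table 7 imputes partial stop dates to month-end or year-end with no upper bound, so AE durations can run past last contact and a washed-out drug can be classed as concomitant

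*SAP*

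**What the plan says.** SAP 6.2.3, Table 7, has three rules for an incomplete resolution date.

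- Year known only: "Use the last date of YYYY to impute the missing month and day of the resolution date".
- Year and month known: "Use the last date of MM to impute the missing day of the resolution date".
- Nothing known: no date is imputed. "The event will be considered ongoing (i.e., not resolved) at the last visit date".

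Neither the table nor its lead-in sets a limit at death, last contact or first dose. Protocol 14.5 says that "completely or partially missing onset and resolution dates will be imputed in a conservative fashion", and extends this to drugs: "Same rules will be followed to impute the completely or partially missing start and end dates of non-study medications".

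Two parts of the SAP use the resulting end dates.

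- SAP 9.1.1 and 9.1.2 summarize durations of ocular inflammation and macular edema, and "only subjects who develop these AEs during the study and later resolved will be used in the duration of AE analysis".
- SAP 4.5.1 sorts drugs by date. A prior medication "is defined as any non-study medication taken and ended prior to the study medication start date". For a concomitant one, "the treatment period (period of time from first dose to last dose) of a concomitant medication taken by a subject must overlap" the study-medication period. SAP 7.5 tabulates both groups.

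**The concern.** Imputing to the end of the known period can only lengthen an interval, and here nothing stops it from passing the end of observation. The table is also uneven. A wholly unknown resolution date goes no further than the last visit, and the event drops out of the resolved-only durations. A partly known date can be placed months later, and the event stays in. Knowing more about an event can therefore give a less plausible date.

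Two descriptive outputs are at stake. Macular edema is an event of special interest. If there are few cases, one year-only date could set the reported maximum and shift the mean duration. In the medication tables, a drug stopped for washout could be listed as taken alongside study treatment.

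**Working it through.** The plan gives no figure that depends on this rule, so there is nothing to reproduce. The check is calendar arithmetic.

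**Inputs from the documents.** The Table 7 rules. Minimum washouts from Protocol 7.4.1: 7 days (miotics, carbonic anhydrase inhibitors), 14 days (alpha agonists, alpha/beta agonists) and 28 days (prostaglandin analogs, beta blockers, alpha-1 blockers, rho kinase inhibitors), each with up to 7 extra days. First dose in the evening of Visit 2 (Protocol 7.1), so first dose date = true stop + washout days. Scheduled visits at Day 91 and Day 361.

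**Assumptions.** Dates are spread evenly over a 365-day year. All percentages are conditional on the date being partial, because the rate of partial dates is not given.

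**1. Days added to an AE.** A true resolution on day k of an m-day month gains m − k days. The mean over the year is the sum of m(m − 1)/2 over the twelve months, divided by 365: (7 × 465 + 4 × 435 + 378)/365 = 5,373/365 = 14.7 days, range 0 to 30. With only the year known, the mean is (365 − 1)/2 = 182 days, range 0 to 364.

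**2. Illustration (invented dates).** Macular edema starts on 10 March 2019, is recorded as resolved in 2019, and last contact is 30 June 2019. Table 7 gives 10 March to 31 December = 297 days inclusive. The longest possible duration is 10 March to 30 June = 113 days.

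**3. How often the imputed date passes the last scheduled visit.** Assume resolution is uniform over a follow-up of L days.

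- Month known: if the visit is on day k of an m-day month, k follow-up days share that month, and month-end falls after the visit unless k = m. The mean count is again 5,373/365 = 14.7. The share is 14.7/91 = 16% for L = 91 and 14.7/361 = 4% for L = 361.
- Year only: the mean count of follow-up days in the visit's calendar year, leaving out a visit on 31 December, is L − L(L − 1)/(2 × 365) − L/365. For L = 91 this is 91 − 11.2 − 0.2 = 79.5, or 87%. For L = 361 it is 361 − 178.0 − 1.0 = 182.0, or 50%.

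A date after the scheduled visit is impossible only if it is also after last contact, because Protocol 12.1.4 allows some events to be followed beyond exit. These shares are therefore upper figures for impossible dates.

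**4. Washed-out drug classed as concomitant.** This happens when the imputed stop is on or after true stop + w, where w is the washout in days. With the month known, the true stop must be on day m − w or earlier. The share is the sum of max(m − w, 0) over the months, divided by 365. With only the year known it is (365 − w)/365.

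| Days from stop to first dose | Month known | Year only |
|---|---|---|
| 7 | 281/365 = 77% | 358/365 = 98% |
| 14 | 197/365 = 54% | 351/365 = 96% |
| 21 (14 + 7) | 113/365 = 31% | 344/365 = 94% |
| 28 | 29/365 = 7.9% | 337/365 = 92% |
| 35 (28 + 7) | 0% | 330/365 = 90% |

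A 7-day class that uses its full window moves to the 14-day row.

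**5. With caps.** In step 2, a last-contact cap gives 113 days. That is still the longest possible value, so the imputation stays conservative. For a washed-out drug, a cap at the day before first dose brings the step 4 shares to 0%. A cap on the day of first dose would fail, because SAP 4.5.1 requires a prior drug to have ended before that day.

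**The case against.** The strongest reply is that the affected records should be few. Protocol 21.3.1 requires start and stop dates for glaucoma drugs used in the 28 days before Visit 1. The site stops the drug at Visit 1 and confirms washout at Visit 2, so a year-only stop date for such a drug would be unusual. Macular edema is reported within 24 hours and followed to an outcome (Protocol 12.1.3, 12.1.4), so its dates should be good. Wholly missing dates never reach the duration summaries, and treating a doubtful drug as concomitant fits the protocol's stated conservative intent.

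Most of this stands, and it limits the size of the point. It does not rescue an end date after the subject was last observed: that is impossible rather than conservative.

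A reader might go further in four ways that the documents do not support.

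- **Washed-out drugs in general become concomitant.** For the 28-day classes with the month known, the share is 0 to 8%.
- **The per-protocol set is distorted.** SAP 5.4 and 7.4 rest exclusions on study-team review of deviations and do not mention imputed dates or the concomitant flag.
- **Primary IOP data are wrongly censored.** SAP 6.2.1 and 8 censor after non-study IOP-lowering or rescue therapy, without tying this to a Table 7 date or to the SAP 4.5.1 classification.
- **There is no cap at the data cut.** SAP 6.5 refers that handling to a separate Data Cut Plan that is not among these documents, so its absence cannot be established.

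It is also fair to object that a blanket cap at first dose could hide an IOP-lowering drug restarted on treatment. Any such cap has to work record by record.

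**Conclusion.** Wrong as written, minor. Table 7 is a stated rule that can return an impossible value, not just an unstated detail. For a partial AE end date the error runs one way: 0 to 30 days with the day missing, 0 to 364 with month and day missing. For a partial stop date of a washed-out drug, false classification as concomitant ranges from 0 to 77% with the month known, depending on washout length, and is about 90 to 98% with only the year known.

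These figures assume dates spread evenly over the year and are conditional on a partial date; the number of such dates is unknown and may be small. The effect is confined to two AE duration summaries and the prior and concomitant medication tables, all descriptive. Treatment-emergent status is untouched, because SAP 4.4.1 defines it by onset date. No effect on the per-protocol set or the primary analysis is shown.

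**What to change.** Add two clauses to Table 7.

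1. Set an imputed end date to the earlier of month-end or year-end and the date of death or last contact. Last contact means the last AE follow-up date, which Protocol 12.1.4 allows to be later than the exit visit.
2. Also cap the imputed stop at the day before first dose for an individual medication record that meets all of these conditions: it is a pre-randomization record of an IOP-lowering drug, the drug started before first dose, washout was confirmed at Visit 2, and the known stop month or year is not later than that of first dose. Do not apply this cap to records of drugs started or restarted after first dose.

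The cost is two clauses and the matching programming. No new data are needed.
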